## **b) Design details**

### **Part Two**

[figure not shown]
This research design refers to the plan or strategy of conducting a six-week content knowledge intervention on students' written test achievements. The experiment design refers to the plan of six specific contents and knowledge that we planned to improve students' written test achievements. The experiment design can be constructed by determining, setting, and establishing variables of students' written test achievements in the experiment. Include independent variable content knowledge, including experimental variables and other variables that exist reliably.

- 1) The first part studies the design process. Next, the research design uses a quantitative research design.

The research design uses a quantitative research design. According to the specific design of the experiment, we intervene with the experimental and choose true experimentally. according to this type of experiment, we adopt type 1 true experimental. It includes the pre-test post-test control group. It combines the samples and periods of the 6-week test on the influence of content knowledge on students' written test achievement and is based on the pre-test post-test control group standard teaching. We focus on students' content knowledge test before the test (before the first week) and after the test (after the sixth week). In the six-week content knowledge intervention, the researcher conducts an experimental and control groups experiment. Individuals in the experimental group receive the experimental treatment, whereas those in the control group do not.

Table 1. Effect of 6-weeks content knowledge workshop on written test performance-  
-research designs

Pre- and Posttest Design		Time →		
Random assignment	standard teaching Group	Pretest Before the first week,	No Treatment	Posttest After the sixth week
Random assignment	Workshop Group	Pretest Before the first week,	Experimental Treatment	Posttest After the sixth week

The second part is an introduction to research and design.

i) Definition of this experiment.

On the one hand, according to the nature of educational evaluation measurement, the experiment belongs to achievement tests because achievement tests are used to examine students' mastery of specific learning experiences that have occurred and to measure students' learning effects (Kellogg, 1997).

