Six weeks' content knowledge is the measurement content. In addition, the test content classification description is based on achievement tests. Achievement tests are divided into comprehensive achievement tests and single-subject achievement tests. Based on the 6-week content knowledge classification, the test belongs to the complete achievement test. Finally, the achievement test is compiled and analyzed. The establishment of achievement tests includes standard teachingized achievement tests and teacher's self-made achievement tests.

This research design is a standard teachingized test because this research achievement test was evaluated by six experts in the field of content knowledge. Six experts, including three American experts and three Chinese content knowledge experts, demonstrated. Three American experts are doctoral supervisors at Ohio State University, and they are essential researchers and discoverers of content knowledge.

ii) Choice is an true experiment.

The experimental control in actual experimental design strictly obeys the three basic principles of repetition, randomization, and local control. In addition, actual experiments comprise the most rigorous and robust experimental methods because of equating the groups through random assignment. In actual experiments, we randomly assign students to workshop groups and standard teaching groups. Individuals in the workshop group receive the experimental treatment, whereas those in the standard teaching group do not. After we administer the treatment, we compile average (or mean) scores on a posttest. One variation on this design is to

obtain pretest as well as posttest measures or observations. When we collect pretest scores, we will compare net scores (the differences between the pre-and post-test).

At the same time, in the design of the influence of 6 weeks' content knowledge on students' written test achievements, we must: a) Randomly select and allocate subjects. b) Accurately manipulate independent variables. c) Strictly control the effect of extra variables or evenly disperse interference variables.

Table 5. Two-way Breakdown of 6-weeks Content Knowledge Design

Content		CAQs	MAQs	T/F AQs	SAQs	EAQs	Knowledge	Understanding	Application	Analysis	Synthesis	Judgment	Score
Sports Training Design	Classify				√	√	-	-	5	5	5	-	15
	Application					√							
Basketball Class Hour Teaching Plan	Objectives				√	√	5	5	-	5	5	-	20
	Contents												
	Steps				√	√							

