### **b) The weaknesses**

i) The random distribution in the true experimental pretest-posttest control group cannot ensure 100% equality between the experimental and control groups.

ii) We adopted the equal group experiment method. Therefore, the most significant possibility is to ensure equality between the workshop group and the standard teaching group. Still, we only

achieved equality between the workshop group and the standard teaching group in the total average number. The weakness lies in not achieving equality in the "mean difference" and "standard teaching deviation."

iii) Group test, the interviewee's reaction is not easy to control. Moreover, it is not easy to analyze the influence of individual students' learning motivation, learning fatigue, and other factors in group tests or examinations. Thus, it is not conducive to diagnosing students' learning situations and the specific guidance of students' learning difficulties.

iv) In the whole experimental design, the independent variables only focus on content knowledge, so more interference variables and interference information are excluded. However, it is challenging to eliminate interference factors, which reduces the precise controllability of the experiment.

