## 12.Data Analysis

Table 12. Data Analysis - Base on Hypothesis

Research Objective	Research Hypothesis	Data Analysis
1.Basic theoretical knowledge	1.1 There is significant difference between the control group and the experimental group in the Sports training design written test performance among P E students in China.	Two-way ANOVA
	1.2 There is significant difference between the control group and the experimental group in the Teaching design written test performance among	Two-way ANOVA

	P E students in China.	
2.Health promotion knowledge	2.1 There is significant difference between the control group and the experimental group in the Muscle function system written test performance among PE students in China.	Two-way ANOVA
	2.2 There is significant difference between the control group and the experimental group in the Exercise physiology system written test performance among PE students in China.	Two-way ANOVA
3.Physical exercise knowledge	3.1 There is significant difference between the control group and the experimental group in the Competition venue planning written test performance Among PE students in China.	Two-way ANOVA
	3.2 There is significant difference between the control group and the experimental group in the Referee rules written test performance among PE students in China.	Two-way ANOVA

Based on the research objective, focus on the research hypothesis. To achieve the research hypothesis, we must use t-way ANOVA analyses.

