Moreover, different selection. The other section is the threat factor of internal effects in the research. Therefore, it is necessary to distinguish the invariable and the extra changeable variable and control the non-experimental facets: one is variable, and the other is unchanged. The varying experimental factors may be a favorite or unfavorable to the experiment. People have biased opinions and different points of view about everything.

Finally, some measures can be taken based on the above collection of the risk of failure during data. But, first, do an excellent job of equal grouping, and control that everything must be the same except the intervention methods of the workshop and standard teaching .

i) We must do an excellent equal group experiment, divided into the workshop and standard teaching groups. Random sampling uses selective measurement and selection methods. First, before the intervention, pre-test measures the original students' content knowledge level. Then, after measurement, they are sorted according to the scores, ranked according to the sequence position, and equally assigned to each group.

ii) People with attitude bias cannot participate in the experiment. If the experimenter finds himself biased, he should avoid wrong opinions.

iii) The experiment must be recorded in detail. The person in charge of the experiment has to make a detailed record of the experiment as a reference for data sources.

iv) We must eliminate the potential confusion of irrelevant variables, make our research reliable, and draw a compelling inference that the relationship between workshop and students' written test achievements.

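### Table 12 names a two-way ANOVA for six simple group comparisons without saying which effect decides them, and no planned comparison conditions on the pretest; ANCOVA on the pretest would settle both.

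*Protocol*

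**What the plan says.** Table 12 (section 12) pairs six hypotheses with a two-way ANOVA. Hypothesis 1.1 is typical: "There is significant difference between the control group and the experimental group in the Sports training design written test performance". None of the six mentions time, change or an interaction. The sentence after the table reads "To achieve the research hypothesis, we must use t-way ANOVA analyses"; since the table gives the two-way form six times, the odd prefix is evidently a slip.

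Section 2 b) describes the design: "It includes the pre-test post-test control group". Table 1 there sets out two groups, each with a pretest before week 1 and a posttest after week 6. Under item ii) of that section two comparisons are described. The first is of posttest means: "After we administer the treatment, we compile average (or mean) scores on a posttest". The second applies where pretests exist: "When we collect pretest scores, we will compare net scores (the differences between the pre-and post-test". Table 12 refers to neither.

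Two further places concern the pretest. Section 13, measure i), says that after the pretest students are handled as follows: "they are sorted according to the scores, ranked according to the sequence position, and equally assigned to each group". Section 10 b) ii) concedes that the design only "achieved equality between the workshop group and the standard teaching group in the total average number".

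**The concern.** The hypotheses have one factor and the named test has two. A two-way ANOVA with group and time as factors gives three tests: group, time and their interaction. A reader who takes the hypotheses literally would report the group main effect. That effect averages the pretest, where no treatment effect can exist, with the posttest, and so estimates half the effect of interest. A reader who starts from the net-score sentence would report the interaction. The text does not choose between them, so the choice could be made after the data are seen.

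Even on the better reading the pretest is used with a coefficient fixed at 1. Neither posttest means nor net scores condition on it, although every student takes it. Two features of this protocol make conditioning the natural choice. Section 13 ranks students on the pretest before grouping them, and a variable that drives allocation belongs in the analysis. The hypotheses are also tested domain by domain, so balance on an overall score, if that is what section 10 b) means, leaves room for imbalance within a domain.

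**Working it through.** **Inputs.** From the protocol: 52 students (section 10 a) iv); two arms; one pretest and one posttest. Assumed, because the protocol gives no value: 26 per arm, true effect d = 0.6 SD, equal pretest and posttest SD of 1, two-sided alpha 5%, pre-post correlation r = 0.3, 0.6, 0.8. There is no stated power or sample-size figure to reproduce.

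**Variance of each estimate**, n per arm:

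- Group main effect: estimates d/2; variance ((1+r)/2)(2/n); 2n−2 df
- Posttest only: estimates d; variance 2/n; 2n−2 df
- Net score, identical to the group-by-time interaction with a within-student error term: estimates d; variance 2(1−r)(2/n); 2n−2 df
- ANCOVA: estimates d; variance (1−r²)(2/n); 2n−3 df

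**Worked case, n = 26, r = 0.6**, with 2/n = 0.0769:

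- Main effect: 0.3 / √(0.8 × 0.0769) = 0.3 / 0.248 = 1.21
- Posttest only: 0.6 / √0.0769 = 0.6 / 0.277 = 2.16
- Net score: 0.6 / √(0.8 × 0.0769) = 0.6 / 0.248 = 2.42
- ANCOVA: 0.6 / √(0.64 × 0.0769) = 0.6 / 0.222 = 2.70

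These ratios are the noncentrality parameters of the t-tests. Power over the range of r:

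| Analysis | r = 0.3 | r = 0.6 | r = 0.8 |
|---|---|---|---|
| Group main effect | 26% | 22% | 20% |
| Posttest only | 56% | 56% | 56% |
| Net score = interaction | 43% | 66% | 92% |
| ANCOVA | 60% | 75% | 94% |

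The net-score standard error is √(2/(1+r)) = 1.24 / 1.12 / 1.05 times that of ANCOVA. The matching sample-size ratio 2/(1+r) means 54 / 25 / 11% more students. These ratios hold for unrestricted randomisation. With 24 per arm (Tables 9 and 10 describe three workshop groups of eight), power is 41 / 62 / 90% for the net score and 57 / 72 / 92% for ANCOVA.

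**Time entered as a non-repeated factor.** Ignoring that the two scores come from one student makes the interaction test far too conservative. Simulated false-positive rates are 1.9 / 0.75 / 0.08% at r = 0.3 / 0.5 / 0.7, against a nominal 5%.

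**Allocation ranked on the pretest.** Section 13 was simulated as random assignment within consecutive ranked pairs (40,000 trials per setting, 26 per arm, no true effect). False-positive rates at r = 0.3 / 0.6 / 0.8 were:

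- Net score: 1.6 / 2.9 / 3.9%
- Posttest only: about 4 / 1.5 / 0.2%
- Group main effect: below 0.2% throughout
- ANCOVA: about 5% throughout

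**Domain imbalance.** If ranking is on a total score that correlates 0.5 to 0.7 with a domain's pretest (assumed), a domain pretest gap above 0.3 SD still arises in about 21% to 13% of simulated trials. A gap g shifts the posttest-only estimate by r·g and the net-score estimate by (r−1)·g. For g = 0.3 SD in favour of the workshop group:

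- Posttest only: +0.09 / +0.18 / +0.24 SD
- Net score: −0.21 / −0.12 / −0.06 SD
- ANCOVA: 0 in expectation

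**The case against.** The strongest defence is that the harmful reading is not the likely one. Table 1 is a group-by-time layout, and section 2 b) says net scores are compared when pretests are collected, which they are. Together these point to the interaction, a valid test that holds its level under simple randomisation. On that view the only gap is that Table 12 does not say so, and ANCOVA is an efficiency preference that could be left to a SAP. This stands in part: the interaction is valid, and at r = 0.8 ANCOVA gains only about 2 points of power. But section 12 prescribes a method for every hypothesis, and that method does not identify one test. That is a method fixed badly, not a detail left for later.

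A second objection is that under exact ranking on the analysed pretest, net-score and ANCOVA estimates have almost the same true sampling SD (for example 0.223 and 0.222 at r = 0.6). That is correct, and the standard-error ratios above do not describe true precision in that case. The net-score test nevertheless reports too large an error, and its power stays lower: about 41 / 68 / 93% against 60 / 76 / 94%.

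Third, assignment within ranked pairs is one interpretation. Section 13 says only that ranked students are assigned equally, while other sections speak of random assignment. The phrase in section 10 b) about the total average is also unclear English. Both cautions are fair, and the results that depend on those readings are conditional on them.

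**Conclusion.** The concern holds. Table 12 does not determine which effect tests the six hypotheses, and the candidates differ in what they estimate: half the effect or all of it, with power of 20–26% against 43–92% under the assumptions used. No planned comparison conditions on the pretest. It is not ignored, since net scores subtract it, but it is not used efficiently. Relative to the interaction, ANCOVA gains about 17 / 9 / 2 points of power at r = 0.3 / 0.6 / 0.8, and of the analyses compared it alone keeps its nominal level if students are allocated in pretest-ranked pairs.

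The sizes rest on the assumed arm split, effect, alpha and correlation. ANCOVA had the highest power at every value tried, including d = 0.5 and d = 0.8. This should be fixed before analysis. It does not invalidate the trial, because a valid test exists within the current wording.

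**What to change.** In Table 12, replace the two-way ANOVA entry for each hypothesis with: ANCOVA of the domain's posttest score on group, adjusted for the pretest score of the same domain; the treatment effect is the adjusted group difference with its 95% confidence interval. Reword each hypothesis as that adjusted difference, and correct the slip in the sentence after the table. In section 2 b) ii), label the posttest-mean and net-score comparisons as sensitivity analyses, and state that pretests are scored by domain, which the protocol implies but does not say outright.

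If ANOVA is kept, specify a mixed (repeated-measures) ANOVA with group between students and time within students. Name the group-by-time interaction as the deciding test and state that it equals the net-score comparison. This removes the ambiguity but not the loss of power.

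The cost is a wording change in sections 2 b) and 12. No new data are needed, since every student already takes the pretest.

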## **10. Experiment the strengths and weaknesses**

### **a) The strengths**

i) True experiments are the most rigorous and robust experimental designs because of equating the groups through random assignment. We randomly sign participants to different conditions of the experimental variable. Individuals in the experimental group (Workshop group) receive the experimental treatment, whereas those in the control group (standard teaching group) do not.

ii) pretest-posttest control-group ensures the equality of experimental (Workshop group) combination control (standard teaching group) group before intervention.

ii) Achievement tests are widely used in educational experiments, and students' achievement tests are the most frequently tested in educational situations. Six weeks' content knowledge is the most basic test for students' written test achievement in an academic position. Generally speaking, after the end of a semester, the achievement tests are conducted, and the achievement tests are used to test later. The scores of students participating in the achievement tests can be compared with the norm data. In this experiment, after learning content knowledge for six weeks, students test it, and the test method and process are the same as achievement tests.

iii) Achievement tests include two types: An academic achievement test and a comprehensive achievement test. A study on the influence of six weeks' content knowledge on complete achievement tests students' achievement. In this study, the content knowledge is classified into six categories, and the comprehensive tests of the six categories meet the comprehensive achievement test standard teachings of achievement tests. The comprehensive achievement test can be either a single test or a complete set of tests. This study's 6-week content knowledge test can use either one of the extensive achievement tests, which is flexible.

iv) Group tests can save human resources and time. We can complete two tests within six weeks and collect 52 students' content, knowledge, achievements, and learning materials within six weeks. Moreover, group tests have been widely used in education.

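### Table 12 names a plain two-way ANOVA with no student term; run as named on group by test occasion, it would ignore that each student is tested twice and could lose much of the power.

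*Protocol*

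**What the plan says.** Table 12 (Protocol section 12) lists six hypotheses, one for each content area, and gives the same method for each, a two-way ANOVA. The sentence below the table repeats the choice with a typing slip: "To achieve the research hypothesis, we must use t-way ANOVA analyses". No factors, error term or repeated-measures structure are given. The hypotheses mention only the group contrast, for example: "There is significant difference between the control group and the experimental group in the Sports training design written test performance".

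The design measures each student twice. Section 2 b) describes the "students' content knowledge test before the test (before the first week) and after the test (after the sixth week"), and Table 1 sets this out as two randomised groups by two test occasions. For the pre-test post-test design, the same section also says "we will compare net scores (the differences between the pre-and post-test"). That is one value per student.

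On size, section 10 a) speaks of two tests and says the study can "collect 52 students' content, knowledge, achievements, and learning materials within six weeks". No arm sizes, alpha, standard deviation or pre-post correlation are stated.

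On allocation, section 2 describes random assignment. Section 13 a) says that after the pre-test, students' results are used as follows: "they are sorted according to the scores, ranked according to the sequence position, and equally assigned to each group".

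**The concern.** Group has two levels. The other factor crossed with it in the design is test occasion, so the natural reading of a two-way ANOVA here is group by occasion on the raw scores. An ordinary two-way ANOVA has a single residual error. With 52 students and two scores each, that error comes from 104 scores in four cells (100 df) and is valid only if a student's two scores are uncorrelated. The protocol itself does not expect that: section 9 v) judges the test credible only if two sittings 1 to 2 weeks apart correlate highly. The correlation across six weeks of teaching may be lower, but zero is not plausible.

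At stake are the conclusions on all six hypotheses. An analyst who follows Table 12 literally could miss a real workshop effect on net scores. If the group main effect is tested instead, a chance difference could be declared significant.

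**Working it through.** **Inputs.** From the protocol: 52 students (section 10 a), two tests each (section 2 b, Table 1), a two-way ANOVA (Table 12). Assumed, because the protocol gives no figure: 26 per arm, equal variances (SD = 1 on both occasions), two-sided alpha 0.05, pre-post correlation r = 0.4, 0.6 and 0.8, and a true net difference of 0.7 SD for power. The protocol has no sample-size or power figure to reproduce.

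**Group-by-occasion contrast** (difference between arms in mean net score).
- Variance used by the ordinary ANOVA: 4/26, so SE = 0.392 whatever the value of r.
- True variance: 4(1 − r)/26.
- Ratio of SEs: 1/√(1 − r).

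Example at r = 0.6. True SE = √(4 × 0.4/26) = 0.248. The ordinary ANOVA (t critical value 1.984 on 100 df) needs an observed net difference of 1.984 × 0.392 = 0.778 SD. The correct test (2.009 on 50 df) needs 2.009 × 0.248 = 0.498 SD. A true effect of 0.7 SD lies below the first threshold and well above the second. Power of the ordinary test is roughly Φ((0.700 − 0.778)/0.248) = Φ(−0.31), or about 38%.

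**Group main effect** (average of both occasions).
- Variance used by the ordinary ANOVA: 1/26.
- True variance under simple randomisation: (1 + r)/26.
- False-positive rate: approximately 2[1 − Φ(1.96/√(1 + r))].

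**Results under simple random assignment** (formulas, confirmed by simulation):

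| | r = 0.4 | r = 0.6 | r = 0.8 |
|---|---|---|---|
| SE overstatement, group-by-occasion | 1.29 | 1.58 | 2.24 |
| False-positive rate, group-by-occasion, ordinary ANOVA | about 1.2% | about 0.2% | about 0% |
| Power at 0.7 SD, ordinary ANOVA | 40% | 38% | 34% |
| Power at 0.7 SD, student as repeated unit | 62% | 79% | 97% |
| False-positive rate, group main effect, ordinary ANOVA | about 10% | about 12% | about 14% |

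**If students are paired on pre-test rank and randomised within pairs** (one reading of section 13 a). The power loss on group-by-occasion remains: at r = 0.6, about 36% against about 81%. The group main-effect test is no longer liberal. Its false-positive rate falls to about 0.3% or lower at these correlations.

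**At r = 0** the two error terms agree and nothing is lost.

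**The case against.** The strongest objection is that the protocol does not write down the faulty model. It gives no factors, no error term and no count of 104 observations, so group by occasion is an inference. The label is often used loosely for a mixed design, and the wording here is loose elsewhere. A SAP, not shown, may state the model. Section 11 mentions stratified sampling by class, which could be a second factor. This stands to a point: a reader might infer from Table 12 that the two scores are counted as independent and that all six tests have wrong standard errors, but the documents do not support that as a statement of fact. The fault is conditional on running the procedure as named on Table 1's layout.

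A second objection is that the net-score comparison in section 2 already respects the pairing. It does, but it does not cure Table 12. Comparing net scores between two groups is a one-way comparison, so the two sections name different analyses and nothing reconciles them.

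Third, the inflated rate for the group effect depends on simple random assignment, and the ranking procedure in section 13 a) can reverse it. This stands, and a general claim that the group test is too liberal would go too far.

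Fourth, arm sizes are not given, and the workshop sessions in Tables 9 and 10 use three groups of eight, which is 24 rather than 26. The degrees of freedom should therefore not be fixed at 50.

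**Conclusion.** The point holds in conditional form. Table 12 fixes a method that, taken as named and applied to the protocol's only two-factor layout, ignores the within-student pairing and departs from the promised net-score comparison. This is more than a detail left for a SAP, because a method is stated for each of the six hypotheses and the literal procedure is the wrong one for twice-tested students.

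With 26 per arm, equal variances, alpha 0.05 and r from 0.4 to 0.8, the main consequence is loss of power on group-by-occasion: about 34% to 40% instead of 62% to 97% for a 0.7 SD net difference. A loss of this kind is present under simple random assignment and under ranked pairs. The false-positive rate of about 10% to 14% for the group main effect applies under simple random assignment only. All these figures rest on assumed correlations. If the intended analysis is already mixed, or uses net scores, the error does not arise and only the wording needs correcting. The change should be made. Confidence is medium, because the intended model is not stated.

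**What to change.** In Table 12 and in the sentence below it, replace the two-way (and t-way) ANOVA with a two-way mixed (split-plot) ANOVA: group between students, test occasion within students, and student as the repeated unit. State that each hypothesis is judged on the group-by-occasion test against the student-within-group error, with n − 2 degrees of freedom (50 if all 52 students are analysed). With two occasions this test is equivalent to comparing net scores between the groups, so it brings Table 12 into line with section 2.

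If allocation is by ranked pairs, the mixed ANOVA is mildly conservative (false-positive rate about 2.0% to 3.9% at the correlations used here), still much closer to 5% than the ordinary test.

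The cost is one line of wording and a different procedure in the same software. No new data and no extra students are needed.
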